# 8.7. Study Termination

[figure not shown]
The study may be stopped at any time by the Investigator and/or Sponsor, with appropriate notification.

# 8.8. Study Duration

An individual subject's participation will involve 8 visits over 6 months.

# 8.9. Monitoring and Quality Assurance

# 9. SAFETY DEFINITIONS, MONITORING AND REPORTING

# 9.1. Adverse Events

An adverse event (AE) is defined as any untoward medical occurrence associated with the use of a drug in humans, whether the event is considered drug related or not. An AE can therefore be any unfavorable and unintended sign (e.g., an abnormal laboratory finding), symptom, or disease occurring after the subject started dosing with the study drug, without any judgment about causality. Any pre-existing medical condition that worsens after administration of the study drug/placebo nasal spray will also be considered a new AE.

AE collection will start following the first administration of the study drug/placebo nasal spray until the last follow up visit of the study.

Documentation regarding the AE should be made as to the nature, date of onset, end date, severity, relationship to study drug, action(s) taken, seriousness, and outcome of any sign or symptom observed by the Investigator or reported by the subject upon indirect questioning.

#### 9.1.1. Severity

Severity of an AE is defined as a qualitative assessment of the degree of intensity of an AE as determined by the Investigator or reported to him/her by the patient/subject. The assessment of severity is made irrespective of relationship to study drug or seriousness of the event and should be evaluated according to the following scale:

- *Mild:* Event is noticeable to the subject but is easily tolerated and does not interfere with the subject's daily activities.
- *Moderate*: Event is bothersome, possibly requiring additional therapy, and may interfere with the subject's daily activities.
- *Severe*: Event is intolerable, necessitates additional therapy or alteration of therapy, and interferes with the subject's daily activities.

## 9.1.2. Relationship to Study Drug

The relationship of each AE to the investigational product should be determined by the Investigator (in a blinded manner) using these explanations:

• *Definite:* When there are good reason and sufficient documentation to demonstrate a direct causal relationship between investigational product and AE

- *Probable:* When there are good reasons and sufficient documentation to assume a causal relationship in the sense of plausible, conceivable, likely but not necessarily highly probable
- *Possible:* When there is sufficient information to accept the possibility of a causal relationship in the sense of not impossible and not unlikely, although the connection is uncertain or doubtful, for example, due to missing data or insufficient evidence.
- *None:* When there is sufficient information to accept a lack of a causal relationship, in the sense of impossible and improbable.
- *Unclassified:* When the causal relationship is not assessable for whatever reason due to insufficient evidence, conflicting data, or poor documentation.

## 9.1.3. Expectedness

The expectedness of an AE should be determined based upon existing safety information about the study drug using these explanations:

- *Unexpected:* An AE that is not listed in the Investigator's Brochure (IB) or is not listed at the specificity or severity that has been observed.
- *Expected:* An AE that is listed in the IB at the specificity and severity that has been observed.
- *Not Applicable:* Any AE that is unrelated to the study drug.

AEs that are mentioned in the IB as occurring with a class of drugs or as anticipated from the pharmacological properties of the drug but are not specifically mentioned as occurring with the drug under investigation are to be considered unexpected.

The Investigator should initially classify the expectedness of an AE, but the final classification is subject to the Medical Monitor's determination.

# 9.2. Serious Adverse Events

An AE is considered a serious adverse event (SAE) if, in the view of either the Investigator or Sponsor, it results in any of the following outcomes:

- Death
- A life-threatening AE

Note: An AE is considered "life-threatening" if, in the view of either the Investigator or Sponsor, its occurrence places the patient or subject at immediate risk of death. It does not include an AE that, had it occurred in a more severe form, might have caused death.

• Inpatient hospitalization or prolongation of existing hospitalization

Note: The term "inpatient hospitalization" refers to any inpatient admission (even if less than 24 hours). For chronic or long-term inpatients, inpatient admission includes transfer within the hospital to an acute/intensive care inpatient unit. Inpatient hospitalization does not include emergency room visits; outpatient/same day/ambulatory procedures; observation/short stay

units; rehabilitation facilities; hospice facilities; nursing homes; or clinical research/phase 1 units.

Note: The term "prolongation of existing hospitalization" refers to any extension of an inpatient hospitalization beyond the stay anticipated or required for the reason for the initial admission as determined by the Investigator or treating physician.

Note: Planned hospital admissions or surgical procedures for an illness or disease that was present before the patient received any study drug are not to be considered SAEs unless the condition deteriorated in an unexpected manner during the trial (e.g., surgery was performed earlier than planned).

• A persistent or significant incapacity or substantial disruption of the ability to conduct normal life functions.

Note: An SAE specifically related to visual threat would be interpreted as any potential impairment or damage to the subject's eyes (e.g., hemorrhage, retinal detachment, central corneal ulcer, or damage to the optic nerve).

A congenital anomaly/birth defect in an offspring of a study subject. •

Important medical events that may not result in death, are life-threatening, or require hospitalization may be considered serious when, based upon appropriate medical judgment, they may jeopardize the patient or subject and may require medical or surgical intervention to prevent one of the outcomes listed in this definition.

SAEs are collected at the time the subject signs the Informed Consent Form until the last follow up visit of the study.

#### 9.3. **Procedures for Reporting Adverse Events**

All AEs and their outcomes must be reported to the Sponsor, and the IRB/IEC as required by the IRB/IEC, federal, state, or local regulations and governing health authorities and recorded on the appropriate eCRF.

#### 9.3.1. **Reporting a Suspected Unexpected Adverse Reaction**

All AEs that are 'suspected' and 'unexpected' are to be reported to the Sponsor and the IRB/IEC as required by the IRB/IEC, federal, state, or local regulations and governing health authorities.

#### 9.3.2. **Reporting a Serious Adverse Event**

To ensure subject safety, all SAEs, regardless of relationship to the study drug, must be reported within 24 hours of the Investigator's knowledge. All information relevant to the SAE must be recorded on the appropriate CRFs. The Investigator is obligated to pursue and obtain information requested by the Sponsor in addition to that information reported on the CRF. All subjects experiencing a SAE must be followed up and the outcome reported.

In the event of a SAE, the Investigator must obtain and maintain in his/her files all pertinent medical records, information, and medical judgments from colleagues who assisted in the treatment and follow-up of the subject; provide the Sponsor with a complete case history, which Confidential

includes a statement as to whether the event was or was not suspected to be related to the use of the study drug; and inform the IRB of the SAE within their guidelines for reporting SAEs.

An SAE will be reported through the electronic data capture (EDC) system. If the EDC system is unavailable to the site staff to report the serious adverse event, the information is to be reported to the sponsor via the SAE Form and submitted to [contact]. The data must be entered into the EDC system when the system is again available. If requested, medical records may be provided at [contact].

# 9.4. Procedures for Unmasking of Study Drug

All subjects, investigators, and study personnel involved with the conduct of the study will be masked with regards to treatment assignments. When medically necessary, the Investigator may need to determine what treatment regimen has been assigned to a subject. When possible (i.e., in non-emergent situations), the Sponsor should be notified before unmasking study drug. Unmasking will be performed utilizing the randomization system. The unmasked subject will continue the study if warranted by the Investigator in consultation with the Medical Monitor.

# 9.5. Type and Duration of the Follow-up of Subjects after Adverse Events

The Investigator will follow unresolved AEs to resolution until the subject is lost to follow-up or until the AE is otherwise classified. Resolution means the subject has returned to baseline state of health or the Investigator does not expect any further improvement or worsening of the AE. If the patient is lost to follow-up, the Investigator should make 3 reasonable attempts to contact the patient via telephone, post, or certified mail. All follow-ups will be documented in the subject's source document. Non-serious AEs identified on the last scheduled contact must be recorded on the AE eCRF with the status noted.

New information relating to a previously reported serious adverse event must be submitted. All new information for serious adverse events must be submitted within 24 hours following the investigator's knowledge of new information. The investigator may be asked to provide additional follow-up information, which may include discharge summary or extracts from the medical record.

# 10. STATISTICAL ANALYSIS

Statistical considerations and methods of analyses for this study are provided below; the accompanying Statistical Analysis Plan (SAP) contains complete details of the planned analyses.

# 10.1. Primary and Secondary Endpoints

## **10.1.1. Primary Endpoint**

• Mean change from baseline in corneal fluorescein staining in subjects with Stage 1 NK at Week 8.

# 10.1.2. Secondary Endpoints

• Mean change in baseline in visual acuity at Week 8

# **10.2.** Analysis Populations

## 10.2.2. Per Protocol

The per-protocol (PP) population will include all ITT subjects with baseline corneal fluorescein staining  $\geq 2$  in subjects with Stage I (corneal epithelial hyperplasia/punctate keratopathy) NK in one or both eyes. Analysis using the PP population will group subjects according to the treatment to which they were randomized.

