# **10.3.** Statistical Hypotheses

Let  $\mu_h$ , and  $\mu_p$  denote the mean change in corneal fluorescein staining from baseline to Week 8 (1.2 mg/mL OC-01 and placebo, respectively) in subjects with Stage 1 NK

H0:  $\mu_h - \mu_p = 0$ H1:  $\mu_h - \mu_p \neq 0$ 

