## 10.5.6. Secondary Efficacy Analysis

The secondary efficacy endpoints are as follows:

• Mean change from baseline in visual acuity at Week 8

The secondary efficacy endpoint will be analyzed on the PP population using an analysis of covariance model comparing the treatment group to placebo with randomization strata, baseline Schirmer's Test Score and the baseline ETDRS visual acuity as covariates.

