#### 5.2 Secondary Efficacy Endpoint

The secondary efficacy endpoint is the mean change from baseline in ETDRS visual acuity at Week 8.

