#### 8 Statistical Hypothesis Testing

Let  $\mu_h$ , and  $\mu_p$  denote the mean change in corneal fluorescein staining from baseline to Week 8 (1.2 mg/mL OC-01 and placebo, respectively) in subjects with Stage 1 NK.

 $H_0$ :  $\mu_h$ - $\mu_p = 0$ 

VS.

 $H_1: \mu_h - \mu_p \neq 0$ 

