#### 9.6 Protocol Deviations

#### 9.7 Subjects Disposition

The number and percentage of subjects randomized and included in each analysis population will be summarized by treatment and overall. Reasons for excluding subjects from the analysis populations will be presented in a by-subject listing.

The number of randomized subjects who completed the study, discontinued early from studydrug, and reasons for discontinuation will be summarized by treatment group and overall.

The Case Report Form (CRF) lists the following reasons why subjects may discontinuetreatment before completing of the study:

- Non-Fatal Adverse Event
- Protocol Violation
- Lost to Follow Up
- Pregnancy
- Disease Progression
- Physician Decision
- Subject Non-Compliance
- Death
- Study Terminated by Sponsor
- Withdrawal by Subject
- Other

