# 9.8 Demographics and Baseline Characteristics

Continuous variables will be summarized using the number of subjects (n), mean, SD, median, 25th and 75th percentiles, and minimum and maximum. Categorical variables will besummarized using counts and percentages. Summary data will be presented by treatment group and overall.

The following demographic will be summarized based on ITT population and Safetypopulation:

- Age
- Gender,
- Ethnicity
- Race

The following baseline ocular assessments will be summarized based on Safety population:

- Pain Visual Analog Scale (VAS)
- Best corrected distance visual acuity (BCDVA)
- Corneal Fluorescein Staining (prior to Schirmer's Test) Modified Oxford GradingScale
- Corneal Sensitivity Mean Score
- Schirmer's Test without Anesthesia

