#### 14.2 Secondary Efficacy Endpoint

The secondary efficacy endpoint is the mean change from baseline in ETDRS visual acuity at Week 8. The secondary efficacy endpoint will be analyzed on the PP population using an analysis of covariance model comparing the treatment group to placebo with the randomization strata, baseline Schirmer's Test Score and the baseline ETDRS visual acuity as the covariates.

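### Is it a fault that visual acuity is tested on a per-protocol set defined by baseline staining of at least 2 rather than by adherence?

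*Protocol*

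**What the plan says.** Protocol 10.2.2 defines the set: "The per-protocol (PP) population will include all ITT subjects with baseline corneal fluorescein staining" of 2 or more, in subjects with Stage I disease in one or both eyes, grouped by randomised treatment. Protocol 5.3 already requires Stage 1 disease for entry, so the staining cut is the only visible restriction beyond ITT.

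For visual acuity, Protocol 10.5.6 says: "The secondary efficacy endpoint will be analyzed on the PP population using an analysis of covariance model comparing the treatment group to placebo". SAP 14.2 agrees: "The secondary efficacy endpoint will be analyzed on the PP population". The covariates are the randomisation strata, baseline Schirmer score and baseline acuity. The same set is the primary one for corneal staining (Protocol 10.5.5, SAP 14.1).

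The endpoint carries no threshold: "The secondary efficacy endpoint is the mean change from baseline in ETDRS visual acuity at Week 8" (SAP 5.2). The hypotheses in Protocol 10.3 concern the "mean change in corneal fluorescein staining from baseline to Week 8 (1.2 mg/mL OC-01 and placebo, respectively) in subjects with Stage 1 NK", and SAP 8 uses the same population: "placebo, respectively) in subjects with Stage 1 NK".

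On reporting, SAP 9.7 states: "The number and percentage of subjects randomized and included in each analysis population will be summarized by treatment and overall". SAP 9.8 summarises demographics on the ITT and Safety populations. For eye measures it says: "The following baseline ocular assessments will be summarized based on Safety population"; the list includes staining and best-corrected acuity.

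**The concern.** Readers take per-protocol to mean subjects who followed the protocol. Here, on the visible definition, it means subjects with enough staining at baseline. A reader could go wrong in two ways: by discounting a randomised comparison as if it were selected after randomisation, or by assuming that adherence was required.

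There is also a question of scope. If some randomised subjects have staining below 2, the acuity test leaves them out, although the endpoint does not. No visible text says why a staining cut suits an acuity endpoint. No baseline table is visibly planned for the tested set. NEI-VFQ-25, another vision outcome, is summarised on ITT (SAP 11). At stake are a narrower population than the stated one and some loss of precision.

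**Working it through.** **1. Does the cut bias the comparison?** Baseline is the last measurement before treatment starts (Protocol 10.5.2, SAP 9.1), and subjects stay in their randomised group (Protocol 10.2.2). Selection therefore cannot depend on treatment received. A subset chosen this way is still a randomised comparison, for a narrower population.

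**2. What could it cost in precision?** The content under Protocol 10.4 and SAP 6 is not visible, so there is no planned figure to reproduce. The one input from the documents is about 50 subjects per arm (Protocol 5.1). Assume a share f of each arm has staining below 2, and equal residual SD in both parts.

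The ANCOVA has five parameters (intercept, treatment, stratum, Schirmer score, baseline acuity). The 95% CI half-width, in residual SD units, is t(0.975, 2n − 5) × √(2/n).

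| Share dropped f | n per arm | Half-width | Ratio to n = 50 |
|---|---|---|---|
| 0 | 50 | 0.397 | 1.000 |
| 5% | 47.5 | 0.408 | 1.027 |
| 10% | 45 | 0.419 | 1.056 |
| 20% | 40 | 0.445 | 1.122 |
| 30% | 35 | 0.477 | 1.202 |
| 40% | 30 | 0.517 | 1.303 |

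**3. Would ITT give the stronger test?** Let k be the treatment effect in low-staining subjects as a fraction of the effect in the rest. The ITT effect is (1 − f) + fk times the PP effect. The PP standard error is larger by 1/√(1 − f). The expected test statistic on ITT relative to PP is therefore

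((1 − f) + fk) / √(1 − f).

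Worked case, f = 0.2 and k = 0.5: (0.8 + 0.1) / 0.894 = 1.006.

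| f | k = 0 | k = 0.5 | k = 1 | Break-even k |
|---|---|---|---|---|
| 10% | 0.949 | 1.001 | 1.054 | 0.487 |
| 20% | 0.894 | 1.006 | 1.118 | 0.472 |
| 30% | 0.837 | 1.016 | 1.195 | 0.456 |
| 40% | 0.775 | 1.033 | 1.291 | 0.436 |

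The break-even is k = (√(1 − f) − (1 − f)) / f. ITT has the larger expected statistic if low-staining subjects respond at least about half as well as the rest, and the smaller one if they respond clearly less. The documents give neither f nor k.

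**4. What can be known from the public text?** Both documents let the SAP prevail (SAP 2, Protocol 10.5). The SAP's contents list 9.2.1 and 9.2.2, but the visible text of SAP 9.2 starts at 9.2.3, so any SAP definition of PP is not visible. The same holds for Protocol 10.2.1, the opening of SAP 14 (which covers primary and secondary endpoints), SAP 14.3 and 14.4, and some eligibility items. In Protocol 10.5.5 the name of the analysis set is cut out. The later sentence there, making PP the primary analysis, suggests that a second staining analysis exists.

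**5. What is already reported?** SAP 9.7 gives the number in each population and lists reasons for exclusion by subject. SAP 9.11.3 gives the acuity treatment difference with a 95% CI, without naming the set. Protocol 10.5.7 summarises acuity on the safety population. The first dose is given in clinic on the day of randomisation (Protocol 7.1.2), so that population should be close to everyone randomised.

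**The case for a change.** The best case for acting is that the remedy is cheap: one more model run on ITT, one baseline table, a descriptive name and a line of rationale. The definition selects those ITT subjects with staining of at least 2, wording that would be unnecessary if entry already required it, so some subjects may well fall below. The acuity paragraphs read as complete and name no second set, unlike the staining paragraph. The descriptive acuity summaries are not visibly the covariate-adjusted ITT estimate.

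Some of this stands. The label is unconventional, and a descriptive name would read better. The visible text gives no reason for using the set for acuity. But wording that hints at low-staining subjects does not show that there are any, and the absence of an ITT run from the visible text is not evidence that none is planned. The hypotheses concern staining only, so their silence on a threshold says little about acuity. Analysis sets are normally defined in the populations section, not inside each endpoint. A reason is also easy to supply: eyes with little staining may have less acuity to regain, and using one set for both tests is coherent.

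**Conclusion.** The reading of the visible text is right, but it shows no error. The acuity test is pre-specified, on a subset fixed at baseline and compared as randomised, which is a legitimate choice in a Phase 2 trial. The cost in precision is nil if nobody has staining below 2. It is about 6% to 30% in CI width if 10% to 40% do, assuming 50 per arm and equal residual SD. Moving to ITT could strengthen or weaken the test, with the break-even at a relative response of about 0.44 to 0.49 over that range. An added ITT model and baseline table would be extra reporting, not a correction, and may duplicate text that is not public. The label matter is one of wording: the definition stands in Protocol 10.2.2, and the counts per population will show how far PP and ITT differ. The plan can be followed as written.

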## 10.2.3. Safety Population

The safety population will include all randomized subjects who received at least one dose of the study drug. Analysis on the safety population will group subjects according to the treatment received.

# **10.3.** Statistical Hypotheses

Let  $\mu_h$ , and  $\mu_p$  denote the mean change in corneal fluorescein staining from baseline to Week 8 (1.2 mg/mL OC-01 and placebo, respectively) in subjects with Stage 1 NK

H0:  $\mu_h - \mu_p = 0$ H1:  $\mu_h - \mu_p \neq 0$ 

# **10.4.** Sample Size and Power Considerations

# **10.5.** Statistical Analysis

This section briefly outlines the planned efficacy analyses. The statistical analysis plan (SAP) describes the methods to be used in detail. If the SAP and the protocol disagree, the details and methods of the SAP will prevail.

## 10.5.1. Randomization and Stratification

Subjects will be randomized 1:1 to receive either OC-01 nasal spray or vehicle control.

The randomization will be stratified by:

• Pre-procedure (Baseline) non-anesthetized Schirmer's score (<5, >5) measured at the screening/randomization visit

A central randomization list will be created using block randomization. Sites will be assigned entire blocks as needed.

# 10.5.2. General Considerations

Quantitative variables will be summarized using the number of subjects (n), mean, SD, median, 25th and 75th percentiles, and minimum and maximum. Qualitative variables will be summarized using counts and percentages.

All summaries will be presented by treatment group. Summaries will be provided for demographics, medical history, concomitant medications, and subject disposition.

For the summaries, medical history, concomitant medications, and AEs will be coded to the Medical Dictionary for Regulatory Activities (MedDRA) and World Health Organization Drug dictionaries, as appropriate.

Baseline measures are defined as the last measure prior to the initiation of study treatment, usually at Visit 1 screening.

# 10.5.3. Unit of Analysis

For safety endpoints, both eyes will be analyzed.

## 10.5.4. Subject Demographics and Baseline Characteristics

Continuous summary statistics will be generated for age in years by treatment group and for all subjects. Discrete summary statistics will be generated for the following qualitative demographic variables: age category, gender, ethnicity, race, and other baseline intranasal examination results, tabulated by treatment group and for all subjects. Individual subject data listings will support the summary tables.

